9.9.10 Change from baseline in [REDACTED] to [REDACTED]

To evaluate the [REDACTED], summary statistics of the [REDACTED] (n, % per [REDACTED] as well as mean, SD, median and range for absolute values and changes from baseline) per visit by treatment group will be tabulated and change from baseline as well as % in each of the [REDACTED] will be graphically presented.

9.9.11 Change from baseline in [REDACTED]

To evaluate the [REDACTED] overtime, summary statistics of the [REDACTED] (n, % per [REDACTED] as well as mean, SD, median and range) per visit by treatment group will be tabulated and the change from baseline as well as % in each of the [REDACTED] will be graphically presented.

9.10 Analysis of safety variables

9.10.1 Adverse events

All AEs captured (i.e., from signature of informed consent up to EOS) are reported in the subject listings based on the SCR, treatment-emergent events are flagged.

Unless otherwise specified, the SAF is used for all analyses of AEs.

An overview of treatment-emergent AEs is presented, per treatment group, as the number and percentage of subjects having any AE, any severe AE, any drug-related AE, any AE leading to study drug discontinuation, any serious AE, any drug-related serious AE, or any fatal serious AE.

Also, AEs are summarized by system organ class and preferred term: Presenting, per treatment group, the number and percentage of subjects having any AE, having an AE in each primary SOC, and having each individual AE (preferred term). SOCs are sorted by descending order of frequency in the ponesimod arm. If the frequencies of SOCs are the same, alphabetical order is used. The same rule applies for preferred terms within SOC. The following summaries are presented:

- Treatment emergent AEs
- Treatment emergent AEs on Day 1
- Treatment emergent AEs on Day 1 of re-initiation, for subjects with at least one re-initiation

- Treatment emergent AEs leading to temporary interruption of study treatment
- Treatment emergent AEs considered to be related to study drug
- Treatment emergent AEs with fatal outcome
- AEs with onset prior to first study drug intake (based on the screened analysis set)
- Post-treatment AEs with onset after EOT + 15 days, for subjects in the post-treatment safety analysis set
- Treatment emergent AEs with onset prior to or at EOT + 1 day

Also, treatment-emergent AEs, treatment-emergent AE related to study treatment, and treatment-emergent AE leading to premature discontinuation of study treatment are summarized by preferred term: presenting, per treatment group, the number and percentage of subjects having any AE, and having each individual AE (preferred term). Preferred terms are sorted by descending order of frequency in the ponesimod arm. If the frequencies are the same, alphabetical order is used.

In addition, one summary table of treatment-emergent AEs by preferred term sorted by absolute percent difference (descending) between ponesimod and teriflunomide is presented.

For all treatment-emergent AEs, the number of occasions (i.e. recurrent events) and corresponding cumulative subject-years of observation, and – based on Poisson regression – the average annualized event rates are tabulated by preferred term sorted by descending rate ratio [see Section 10.1].

Treatment-emergent AEs by maximum intensity are summarized by presenting, per treatment group, the number and percentage of subjects having any AE, and having each individual AE (preferred term).

For the disclosure of the results to EudraCT and ClinicalTrials.gov (and inclusion in the clinical study report appendix), frequent treatment emergent non-serious AEs, i.e., preferred terms reported in $\geq 5\%$ of subjects in at least one treatment group, are summarized as follows:

- 1) The number and percentage of subjects having any frequent non-serious AE, and having each individual non-serious AE (preferred term).
- 2) The overall number of frequent non-serious AEs (i.e., reported episodes), and the number and percentage of frequent AEs (preferred term). Here the denominator is the overall number of frequent non-serious AEs.

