Subjects who prematurely discontinue study treatment enter the PTOp period. It lasts from last dose of study drug until 108 weeks after randomization (i.e., end of planned treatment period) with 12-weekly visits as per the original visit schedule. Safety follow-up visits are conducted in addition, following the post-treatment safety follow-up period schedule.

Table 1 Dosing scheme

Treatment period	Duration	Dose regimen in the ponesimod group	Dose regimen in the teriflunomide group
Titration	Day 1 and 2	2 mg	14 mg
Titration	Day 3 and 4	3 mg	14 mg
Titration	Day 5 and 6	4 mg	14 mg
Titration	Day 7	5 mg	14 mg
Titration	Day 8	6 mg	14 mg
Titration	Day 9	7 mg	14 mg
Titration	Day 10	8 mg	14 mg
Titration	Day 11	9 mg	14 mg
Titration	Day 12 to 14	10 mg	14 mg
Maintenance	Day 15 until EOT*	20 mg	14 mg

*Visit 4 is to take place at Day 15 ± 1 day. The titration kit will therefore include an additional capsule and tablet (if applicable) for treatment on Day 15 (i.e., dose regimen in the ponesimod group = 10 mg). Dosing scheme during re-initiation following treatment interruption of > 3 days follows the same titration dosing scheme.
EOT = End-of-Treatment.

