5.1.6 Subject study completion status

A subject is considered to have completed the study as per the corresponding entry on the 'End of Study' eCRF ("Did the subject complete the study?" answered with "Yes"). All subjects not completing the study are considered to have prematurely discontinued the study.

Note: A subject who prematurely discontinued study treatment but completed the PTOp is considered to have completed the study according to the protocol.

The End-of-Study (EOS) date is defined as the 'Date of End of Study' collected on the end of study eCRF, unless a subject is lost to follow-up or dies, in which case 'Date of Last Contact' from the end-of-study eCRF or 'Date of Death' from Death eCRF are used. If missing, the last recorded visit date (i.e., the latest assessment date within any visit) is considered as the EOS date.

For subjects completing the 108 weeks of treatment and entering the extension study, the EOS visit should occur at the FU1 visit (scheduled 14–22 days after last drug intake), or at the abbreviated FU2 visit if available (scheduled 23–37 days after last drug intake). For subjects completing the 108 weeks of treatment and not entering the extension study, the EOS visit corresponds to the FU2 visit (scheduled 30–37 days after last drug intake). For subjects prematurely discontinuing study treatment, EOS is scheduled to be the Week 108 visit (Visit 14A – W108A – Week 108).

For subjects prematurely discontinuing the study, reasons for premature discontinuation from study are: ‘Death’, ‘Lost to follow-up’, ‘Subject decision’ (further split into ‘Withdrawal of consent’, ‘Tolerability related’, ‘Efficacy related’, and ‘Other’), ‘Physician decision’ (further split into ‘Adverse event’ and ‘Other’) or ‘Sponsor decision’ (further split into ‘Study terminated’ and ‘Other’). Whenever ‘Other’ is selected, free text can be provided in addition. An additional category ‘Reason not provided’ is defined for subjects where the reason is missing.

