5.5.2.1 Frequency and prevalence of adverse events

AEs are summarized according to both frequency and prevalence and based on various grouping terms (for example MedDRA preferred term, or MedDRA primary system organ class).

For frequency of subjects experiencing an AE, AEs reported more than once for a subject (based on grouping term) are counted only once per subject.

For total cumulative number of events, multiple records of the same MedDRA preferred term in the AE dataset for the same subject count as individual events (episodes of the same type of event) unless they have the same start date and – if available – time.

The observation time (in days) per subject for summaries of treatment-emergent AEs is calculated as: minimum (EOT + 15, EOS) – study treatment start date + 1.

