7.1.5 Other analysis sets

The following other analysis sets are defined:

7.1.5.1 *Non-conventional MRI sub-study full analysis set*

Includes all subjects in the full analysis set who have consented to participate in the non-conventional MRI techniques sub-study ('Non-conventional MRI techniques sub-study' ticked on 'Informed Consent' eCRF).

7.1.5.2 *Patient preference sub-study full analysis set*

Includes all subjects in the full analysis set who have consented to participate in the Patient Preference sub-study ('Patient Preference Questionnaire' ticked on 'Informed Consent' eCRF).

7.1.5.3 *DL_{CO} sub-study safety analysis set*

Includes all subjects in the safety set who have consented to participate in the DL_{CO} sub-study ('DL_{CO} sub-study' ticked on 'Informed Consent' eCRF). Subjects are summarized in the same treatment group as in the safety analysis set.

7.1.5.4 *Post-treatment observation period analysis set (PTOP Set)*

Includes all subjects in the full analysis set who prematurely discontinued treatment (see definition in Section 5.1.5), with EOS date after EOT + 7 days.

7.1.5.5 *Post-treatment safety analysis set*

Includes all subjects in the safety analysis set who have an EOS date > EOT + 15 days. Subjects are summarized in the same treatment group as in the safety analysis set.

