9.6.5.6 ARR post EOT + 7 days following premature treatment discontinuation

This analysis is similar to the analysis described for the primary efficacy variable, using a model with the number of confirmed relapses in the PTO as a response variable, treatment, stratification variables and the number of relapses in the year prior to study (≤ 1 [or missing] and ≥ 2) entry as factors and the logarithm of time between EOT + 8 days and EOS (in years) as an offset variable. The analysis is based on the Post-treatment observation period analysis set (FAS subjects prematurely discontinuing treatment with EOS date after EOT + 7 days).

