9.10.2.2 Serious adverse events (SAEs)

Unless otherwise specified, the SAF is used for all analyses of SAEs.

SAEs are summarized by SOC and preferred term. The following summaries are presented:

- Treatment emergent SAEs
- Treatment emergent SAEs on Day 1
- Treatment emergent SAEs on Day 1 of re-initiation, for subjects with at least one re-initiation
- Treatment emergent SAEs with fatal outcome
- Treatment emergent SAEs with fatal outcome considered to be related to study drug
- Treatment emergent SAEs considered to be related to study drug
- Treatment emergent SAEs leading to study drug interruption
- SAEs with onset prior to first study drug intake (based on the screened analysis set)
- Post-treatment SAEs with onset after EOT + 15 days, for subjects in the post-treatment safety analysis set.

In addition, treatment-emergent SAEs, treatment-emergent SAE related to study treatment, and treatment-emergent SAE leading to premature discontinuation of study treatment are summarized by preferred term.

For the disclosure of the results to EudraCT and ClinicalTrials.gov (and for inclusion in the clinical study report appendix), the overall number of treatment emergent SAEs (i.e., reported episodes), and the number and percentage SAEs (preferred term) are summarized. Percentages of subjects are based on the number of subjects in the safety analysis set and the percentages of events are based on the total number of events.

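### Post-treatment AEs and SAEs are shown only as crude percentages in one set that pools completers with 1–22 days at risk and early stoppers with up to about 740 days

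*SAP*

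**What the plan says.** The denominator is the post-treatment safety analysis set of SAP 7.1.5.5: "Includes all subjects in the safety analysis set who have an EOS date" later than EOT + 15 days. Completion of treatment plays no part in the definition.

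Two tables use this set. In 9.10.1 it is "Post-treatment AEs with onset after EOT + 15 days, for subjects in the post-treatment safety analysis set"; in 9.10.2.2 it is "Post-treatment SAEs with onset after EOT + 15 days, for subjects in the post-treatment safety analysis set". Both are system organ class and preferred term tables, for which 9.10.1 specifies the number and percentage of subjects per arm.

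Time-adjusted AE summaries stop at the treatment-emergent window. Section 9.10.1 plans "For all treatment-emergent AEs, the number of occasions (i.e. recurrent events) and corresponding cumulative subject-years of observation", with Poisson annualised rates, and 9.10.2.4 does the same for treatment-emergent AESIs and MACE. Section 5.5.2.1 introduces its only definition with "The observation time (in days) per subject for summaries of treatment-emergent AEs is calculated as" and ends that time at the earlier of EOT + 15 and EOS.

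Follow-up length is fixed in 2.1.1, 5.1.6 and 5.4.1. Completers entering the extension leave at FU1 (14–22 days after last dose) "or at the abbreviated FU2 visit if available" (23–37 days). Other completers leave at FU2 (30–37 days). For premature discontinuers there is the post-treatment observation period (PTOP): "It lasts from last dose of study drug until 108 weeks after randomization". AEs are captured up to EOS, so PTOP events enter these tables.

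**The concern.** A percentage of subjects with an event compares arms fairly only if time at risk is similar. Here it varies within one table from a day to about two years, according to whether and when the subject stopped treatment. Those are post-randomisation outcomes that treatment can affect. A by-arm difference can appear, or be hidden, purely through differences in early stopping, its timing or PTOP retention.

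The SAP deals with the same structure elsewhere. For relapses after EOT + 7 days, 9.6.5.6 restricts the analysis to premature discontinuers and uses "the logarithm of time between EOT + 8 days and EOS (in years) as an offset variable". Section 4.3 keeps PTOP data out of the reversibility endpoints and limits them to EOT + 37 days. Neither approach is carried over to post-treatment AEs and SAEs, although these two tables are the only planned system organ class and preferred term summaries of events starting after EOT + 15 days.

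**Working it through.** The SAP states no figure for post-treatment time at risk, so there is none to reproduce.

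**Step 1. Days at risk from the SAP's own windows.** Days at risk = EOS − (EOT + 15).

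| Group | EOS, days after EOT | Days at risk |
|---|---|---|
| Completer, extension, FU1 | 14–22 | 1–7 (FU1 on day 14 or 15 falls outside the set) |
| Completer, extension, abbreviated FU2 | 23–37 | 8–22 |
| Completer, no extension, FU2 | 30–37 | 15–22 |
| Premature discontinuer, PTOP | to Week 108 (day 756) | up to 756 − 15 = 741 |

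A discontinuer whose last dose is at Week 24 (day 168), with EOS on day 757, has 757 − (168 + 15) = 574 days. At Week 60 the figure is 322 and at Week 96 it is 70. Table 3 targets FU1 at last intake + 15 days, so an extension entrant seen exactly on target is not in the set. A few days of visit timing decide who is counted.

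**Step 2. Effect on the crude percentage.** Every input from here on is an assumption, because the SAP gives no early-stopping, extension-entry or PTOP-retention figures by arm. The true AE rate r is the same in both arms, constant over time.

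Percentage = Σ w·(1 − exp(−r·t/365.25)) / Σ w, over four groups:

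- FU1 exits in the set: w = (1 − d)·e·(1 − f)·(1 − x), t = 4
- abbreviated FU2: w = (1 − d)·e·f, t = 15
- completers not entering the extension: w = (1 − d)·(1 − e), t = 18.5
- early stoppers in the set: w = d·q, t = T

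Here d is the share stopping early, e the share of completers entering the extension, f the share of those with abbreviated FU2, x the share of FU1 exits outside the set, and q the share of early stoppers in the set.

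**Step 3. Central case.** e = 0.8, f = 0.1, x = 0.35, q = 0.8, T = 180, r = 1 per year. For d = 0.15 the weights are 0.3978, 0.068, 0.17 and 0.12 (sum 0.7558), and the event probabilities are 0.0109, 0.0402, 0.0494 and 0.3891. The weighted mean is 8.2%.

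| Early stopping d | r = 1 per year | r = 0.3 per year |
|---|---|---|
| 12% | 7.1% | 2.4% |
| 15% | 8.2% | 2.8% |
| 20% | 10.1% | 3.5% |

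At d = 0.15, early stoppers are 0.12/0.7558 = 16% of the set but supply 79% of its person-time. Holding d at 15% and r at 1 per year, T = 90, 180 and 365 gives 5.5%, 8.2% and 12.1%.

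**Step 4. Grid.** r = 0.3, 1, 2; e = 0.6, 0.8, 0.9; f = 0.05, 0.2; x = 0.2, 0.5; q = 0.5, 0.8, 1; T = 60, 180, 365.

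| Arms compared, equal true rate | Spurious difference (points) | Spurious ratio |
|---|---|---|
| 15% vs 20% stop early | 0.1 to 5.6 | 1.09 to 1.30 |
| 12% vs 20% stop early | 0.2 to 9.2 | 1.14 to 1.57 |
| 15% in both, T = 180 vs 365 | 1.1 to 5.7 | – |
| Everything equal | 0 | 1 |

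Across the grid, early stoppers supply 28% to 96% of person-time.

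**The case against.** The SAP is internally consistent here: set, cut-off and statistic agree, and no test, ratio or interval is attached to these two tables. The comparative AE analysis is the treatment-emergent one, which does have rates. Reporting n (%) for post-treatment events is common.

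The reader also gets context by arm: time in study, time on treatment and reasons for stopping (9.3.1), the size of each analysis set including the PTOP set (9.3.3), DMTs started after EOT + 7 days (9.4.5.1), deaths more than 15 days after treatment (9.10.2.1), and a listing of every AE.

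The magnitude is assumed throughout. Most rows are single terms: at an assumed 0.02 events per year, the central case gives only about 0.20% versus 0.25% for 15% versus 20% stopping. Finally, completion status is itself post-randomisation, and PTOP time mixes off-drug time with new DMTs, so a rate does not restore a randomised comparison.

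Most of this stands as a limit on importance. The displays cited show whether early stopping differs between arms, but give no post-treatment time at risk and no rate for these tables. The single-term gap is small in points, yet the ratio remains about 1.25. The last point argues against a single pooled rate and for rates within each group, read descriptively.

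**Conclusion.** The concern holds. The pooling, the n (%) format, the lack of any post-treatment observation time and the two ranges of days at risk all follow directly from the SAP. The percentages can show a by-arm difference with no difference in risk. How large, and in which direction, cannot be known from this document: the 0.1 to 5.6 and 0.2 to 9.2 point ranges rest entirely on assumed inputs and a constant rate, and there is no distortion if stopping, timing and retention are alike in both arms. The tables are descriptive. The primary, secondary and treatment-emergent safety analyses are unaffected. It should be changed because it is cheap and the present display is hard to interpret.

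**What to change.** - In 5.5.2.1, define post-treatment observation time as EOS − (EOT + 15) days for subjects in the post-treatment safety analysis set.
- In 9.10.1 and 9.10.2.2, present the post-treatment AE and SAE tables separately for treatment completers (safety follow-up only, to EOT + 37 days) and for premature discontinuers (PTOP).
- Within each group and arm, add cumulative subject-years and events per 100 subject-years beside n (%). Do not give one pooled rate.

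The cost is SAP wording, one split and a few extra columns, all from dates already derived; no new data are needed. The drawbacks are small event counts among completers and rates that assume a roughly constant hazard within each group, although other DMTs may start in the PTOP. A footnote should say so, and should add that the groups are defined after randomisation.

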9.10.2 Deaths, other serious adverse events

9.10.2.1 Death

The number and percentage of subjects who died are summarized per treatment group, including the reported primary cause of death. A summary table is provided for all deaths

overall and split by time of death (treatment-emergent and more than 15 days after end of study treatment).

A separate listing including all deaths is provided based on the SCR; treatment-emergent deaths are flagged as such in that listing.

9.10.2.2 Serious adverse events (SAEs)

Unless otherwise specified, the SAF is used for all analyses of SAEs.

SAEs are summarized by SOC and preferred term. The following summaries are presented:

- Treatment emergent SAEs
- Treatment emergent SAEs on Day 1
- Treatment emergent SAEs on Day 1 of re-initiation, for subjects with at least one re-initiation
- Treatment emergent SAEs with fatal outcome
- Treatment emergent SAEs with fatal outcome considered to be related to study drug
- Treatment emergent SAEs considered to be related to study drug
- Treatment emergent SAEs leading to study drug interruption
- SAEs with onset prior to first study drug intake (based on the screened analysis set)
- Post-treatment SAEs with onset after EOT + 15 days, for subjects in the post-treatment safety analysis set.

In addition, treatment-emergent SAEs, treatment-emergent SAE related to study treatment, and treatment-emergent SAE leading to premature discontinuation of study treatment are summarized by preferred term.

For the disclosure of the results to EudraCT and ClinicalTrials.gov (and for inclusion in the clinical study report appendix), the overall number of treatment emergent SAEs (i.e., reported episodes), and the number and percentage SAEs (preferred term) are summarized. Percentages of subjects are based on the number of subjects in the safety analysis set and the percentages of events are based on the total number of events.

9.10.2.3 Treatment-emergent adverse events leading to study treatment discontinuation

The SAF is used for all analyses of (S)AEs leading to discontinuation. AEs and SAEs leading to premature discontinuation of study drug are summarized by SOC and preferred term. The following summaries are presented:

- Treatment-emergent AEs leading to premature discontinuation of study drug
- Treatment-emergent AEs leading to premature discontinuation of study drug on treatment day 1
- Treatment-emergent AEs leading to premature discontinuation of study drug on Day 1 of re-initiation, for subjects with at least one re-initiation

- Treatment-emergent SAEs leading to premature discontinuation of study drug
- Treatment-emergent SAEs leading to premature discontinuation of study drug on treatment day 1
- Treatment-emergent SAEs leading to premature discontinuation of study drug on Day 1 of re-initiation, for subjects with at least one re-initiation

In addition, treatment-emergent AEs leading to premature discontinuation of study drug are summarized by preferred term.

9.10.2.4 Other significant adverse events

9.10.2.4.1 Adverse events of special interest (AESIs)

For each of the AESI categories described in Section 5.5.9.1, the following information is presented: The number and percent of subjects with AESI is summarized by preferred term per treatment arm. In addition, the number and percentage of subjects having any event of that category, having any serious event, any fatal event or any event leading to premature discontinuation of study drug, the relative risk relative to teriflunomide (incl. 95% CI). The table will also include key estimates from a time to first event analysis (Kaplan-Meier estimates and hazard ratio along with 95% CI), the number of occasions (i.e., recurrent events) and corresponding cumulative subject-years of observation, and based on Poisson regression, the average annualized event rate and rate ratio with corresponding rate ratio incl. 95% CI. Corresponding time to first event (Kaplan-Meier) curves (going upwards) are graphically displayed as described in Section 10.4. Separate listings are prepared on the FAS.

These tables and graph are presented for the following subcategories:

- Treatment-emergent AESIs, based on the SAF for each AESI category separately;
- Hepatobiliary disorders / Liver enzyme abnormality AESI that occurred after start of study drug and up to and including EOT + 1 day

In addition, treatment-emergent AESI Effect on heart rate and rhythm related AEs are summarized by time of onset by presenting, per treatment group, the number and percentage of subjects having any AE, and having each individual AE (preferred term). Preferred terms are sorted by descending order of frequency in the ponesimod arm. This analysis is done

- By day of onset after study start, by groups: Day 1, Day 2, Day 3, Day 4, Day 5, Day 6, Day 7, Day 8, Day 9, Day 10, Day 11, Day 12, Day 13, Day 14, Day 15, Day 16, > Day 16

- By day of onset after any re-initiation of up-titration, for the following (daily) by groups: Day 1 of any re-initiation, Day 2 of any re-initiation... , Day 16 of any re-initiation

9.10.2.4.2 *Major adverse cardiovascular events (MACE)*

Based on the SAF, treatment emergent MACEs are summarized by presenting, per treatment group, the number and percentage of subjects having any MACE, and having an event of the MACE subcategories (cardiovascular death, non-fatal myocardial infarction, non-fatal stroke), and the relative risk relative to teriflunomide (including 95% CI). The table will also include key estimates from a time to first event analysis (Kaplan-Meier estimates and hazard ratio along with 95% CI), the number of occasions (i.e., recurrent events) and corresponding cumulative subject-years of observation, the average annualized event rate and corresponding Poisson rate ratio including 95% CI. Corresponding time to first event (Kaplan-Meier) curves are graphically displayed as described in Section 10.4. A listing is prepared.

9.10.3 **Electrocardiography (ECG)**

The following summary displays are provided by treatment group, all based on the SAF:

- Quantitative ECG results and absolute change from baseline, as described in Section 5.5.11.1, are summarized, by parameter and visit. Except for data summarized under ‘Baseline’, ‘Day-15 follow-up’ and ‘Day-30 follow-up’, only treatment-emergent results from nominal scheduled visits are included, premature EOT visit is mapped to a scheduled visit [see Section 11.3]. These are summarized descriptively and mean changes (with standard error) from baseline in heart rate are also presented graphically over time (plots starting with zero change at baseline);
- Quantitative ECG results and absolute change from pre-dose on Day 1, by time point (pre-dose, 1–12 hours post dose), are summarized descriptively and mean changes (with standard error) from pre-dose in heart rate are also presented graphically over time (plots starting with zero change at pre-dose), plots are only to include Hours 1–4;
- Descriptive summary statistics of quantitative ECG result and absolute change from pre-dose on Day 1 of first Re-initiation, by time point (pre-dose, 1– 12 hours post dose); Note: Data from re-initiations beyond the first are listed only;
- Number and percentage of subjects with any treatment-emergent PR, QTcF prolongations and HR outliers together with 95% CIs for proportions (Clopper-Pearson exact method) are presented overall and by visit. Percentages are based on the number of subjects with at least one treatment emergent result available for the corresponding parameter. Abnormalities are presented cumulatively, i.e., a subject with a treatment emergent QTcF result > 500 ms is also summarized in the category QTcF > 450 ms;

- Number and percentage of subjects with any post-dose PR, QTcF prolongations and HR outliers on Day 1 or Day 1 of Re-initiation together with 95% CIs for proportions (Clopper-Pearson exact method) are presented overall post-dose hours and by individual time point. Percentages are based on the number of subjects with at least one post-dose result available for the corresponding parameter and time point. Abnormalities are presented cumulatively;
- Number and percentage of subjects with any 3-hr post-dose PR, QTcF prolongations and HR outliers on Day 1, Week 12 Visit, and Day 1 of any re-initiation together with 95% CIs for proportions (Clopper-Pearson exact method). For this analysis the ECG results reported as 3-hours post-dose are considered, irrespective of actual time the ECG was performed. Percentages are based on the number of subjects with a result available for the corresponding parameter at 3-hours post-dose. Abnormalities are presented cumulatively;
- Number and percentage of subjects with prior morphological ECG findings, and new/pre-existing treatment-emergent morphological ECG findings (at any time during the respective periods, i.e., prior or treatment-emergent), by abnormality and group term following CDISC terminology are presented. New (as compared to any assessment prior to study drug start) findings are also presented by visit;
- Number and percentage of subjects with prior and new/pre-existing morphological ECG findings on Day 1 or on Day 1 of any re-initiation, by abnormality and group term following CDISC terminology are presented. New (as compared to any assessment prior to study drug start) post-dose hourly ECG findings are also presented and by individual time point;
- Number and percentage of subjects with prior and new/pre-existing treatment-emergent morphological ECG findings at Visit 4 (Week 2), by abnormality and group term following CDISC terminology.

All ECG data including QTc parameters are listed by treatment group and subject based on the SCR. All marked abnormalities are flagged and morphological findings are listed.

